5.1.5.3.1 Multiple Imputation (MI) and MCMC Method

The multiple imputation assume that the missing data are missing at random (MAR), that is, the probability that an observation is missing may depend on the observed values but not the missing values. It also assumes that the parameters q of the data model and the parameters f of the missing data indicators are distinct. That is, knowing the values of q does not provide any additional information about f , and vice versa. If both MAR and the distinctness assumptions are satisfied, the missing data mechanism is said to be ignorable. The MI procedure provides three methods for imputing missing values and the method of choice depends on the type of missing data pattern. For monotone missing data patterns, either a parametric regression method that assumes multivariate normality or a nonparametric method that uses propensity scores is appropriate. For an arbitrary missing data pattern, a Markov chain Monte Carlo (MCMC) method that assumes multivariate normality can be used.

In MCMC, one constructs a Markov chain long enough for the distribution of the elements to stabilize to a common, stationary distribution. By repeatedly simulating steps of the chain, it simulates draws from the distribution of interest.

In Bayesian inference, information about unknown parameters is expressed in the form of a posterior distribution. MCMC has been applied as a method for exploring posterior distributions in Bayesian inference. That is, through MCMC, one can simulate the entire joint distribution of the unknown quantities and obtain simulation-based estimates of posterior parameters that are of interest.

Assuming that the data are from a multivariate normal distribution, data augmentation is applied to Bayesian inference with missing data by repeating a series of imputation and posterior steps. These two steps are iterated long enough for the results to be reliable for a multiply imputed data set (Schafer 1997). The goal is to have the iterations converge to their stationary distribution and then to simulate an approximately independent draw of the missing values.

Sample SAS code for MI using MCMC method will be provided as instruction to TFLs.

Further, as a sensitivity analysis, the pattern-mixture model approach is used to model the distribution of a response as the mixture of a distribution of the observed responses and a

distribution of the missing responses, for which the missing values can be imputed under a plausible scenario for which the missing data are missing not at random. The control-based pattern imputation, in which, the set of observations from control group are used to derive the imputation model.

5.1.5.3.2 Multiple imputation sensitivity analyses steps

The following steps are followed, in order to create the structure of the analysis dataset where missing values and appropriate variables could be imputed.

- Obtain subject id, treatment group (trt01pn), stratification factors (prior migraine prophylactic treatment failed, medication overuse), sex, race group, age group, BMI group from ADSL
- Obtain number of prior migraine prophylactic treatment failed and baseline disease duration from ADBS
- Obtain avisitn paramcd param avalc base chg dtype from ADATTACK
- Perform minor data manipulation, as required, to reinstate the missing data, eg if dtype="BOCF" then aval=., avalc="" and chg=.
- Ensure the baseline values are included in the chg variables, e.g. if avisitn=2000 then chg=base
- Transpose all the data so you have one observation per subject and each visit becomes a variable within its own right, e.g. rows where avisitn=2004, 2008, 2012 become the column wk4, wk8, wk12.
- Impute the missing data for MAR and MNAR separately according to the methods in next steps

MAR multiple imputations steps:

Note that some variables (for ex., duration of migraine) might have missing values and there is a mix of categorical and continuous variables in the modelling of the missing data. Therefore, fully conditional specification (FCS) methods are employed within proc mi to impute the missing data.

- FCS logistic is used for dichotomous variables; discrim is used for categorical variables with more than 2 categories; regpmm is used for continuous variables.
- wk0, wk4, wk8 and wk12 represent the chg variable for each of the visits respectively, where wk0 is baseline.

MNAR multiple imputations steps:

- Here is an implementation of the pattern-mixture model approach that uses a control-based pattern imputation and imputing the missing data step-by-step, where the baseline variables inform on any missing baseline efficacy values. The baseline efficacy values then inform on the next visit, which then informs on the next visit and so on until all visits have non-missing data.

- Furthermore, an option is used at post-baseline visits (modelobs= (trt01p='Placebo')) to include an adjustment for the fact that any missing data from active treatment subjects will be similar to placebo subjects under the assumption that missing values in the active treatment subjects implies they are no longer on treatment. That is, an imputation model for the missing data in the active treatment group is constructed not from the observed data in the active treatment group but rather from the observed data in the placebo group. This model is also the imputation model that is used to impute missing data in the placebo group.

MAR and MNAR modeling step:

- For the change from baseline in MMD analysis, it uses a linear mixed effects repeated measures model on imputing data under the assumption of MAR or MNAR. There is no gaps in imputed data, therefore, all the data is available to analyze and can use a fixed effects model looking only at the avisitn=2012/week12 data.
- If necessary, for the 50% Responders analysis, it is based on imputed MMD data under the assumption of MAR or MNAR. Then, use the same method as for primary analysis - the stratified CMH test to get estimates for numbers of responders in each treatment group and odds ratio at week 12 for each dataset.

MAR and MNAR combining step:

- The output dataset with the treatment LS means (LSMEANS) and the treatment differences (DIFF) are then sorted, manipulated and read into proc mianalyze to combine the individual sets of imputed results into one set of overall results, see all steps SAS codes in TFLs document.

5.2 AEs coding/grading

Adverse events are coded using the Medical dictionary for regulatory activities (MedDRA) terminology.

Adverse event severity is graded based on NCI Common Toxicity Criteria version 4 or higher, which is available at the following: http://evs.nci.nih.gov/ftp1/CTCAE/CTCAE_4.03_2010-06-14_QuickReference_5x7.pdf

The CTCAE displays Grades 1 through 5 with unique clinical descriptions of severity for each AE based on this general guideline:

Grade 1 - Mild; asymptomatic or mild symptoms; clinical or diagnostic observations only; intervention not indicated.

Grade 2 - Moderate; minimal, local or noninvasive intervention indicated;

Grade 3 - Severe or medically significant but not immediately life-threatening; hospitalization or prolongation of hospitalization indicated; disabling;

Grade 4 - Life-threatening consequences; urgent intervention indicated.

Grade 5 – Death related to AE.

5.3 Statistical models

5.3.1 Van Elteren Test for Continuous Response Variable with Strata

When assumption of normality in analysis of covariance model is violated, then a Van Elteren's test for stratified continuous data can be used. Van Elteren's test is a nonparametric test that compares treatments in the presence of blocking. The test is an extension of Wilcoxon's rank-sum test ([Van Elteren 1960](#)).

Van Elteren proposed to combine stratum-specific Wilcoxon rank-sum statistics with weights inversely proportional to stratum size.

Suppose that the data obtained for the subjects in two treatment groups are split into J strata. Then, the stratified Wilcoxon test statistic is

$$W^* = \frac{\sum_{j=1}^J a_j (T_j - E(T_j))}{\sqrt{\sum_{j=1}^J a_j^2 Var(T_j)}}$$

where $j=1,..,J$ denote the strata, $(T_j - E(T_j))$ and $\sqrt{Var(T_j)}$ are the numerator and denominator respectively of the Wilcoxon statistic for the data in strata j and a_j is the weight applied to each strata. The test statistic can be rewritten in the form

$$W^* = \frac{\sum_{j=1}^J a_j \sqrt{\frac{n_{0j} n_{1j}}{n_{0j} + n_{1j}} \left(\frac{1}{n_{0j}} \sum_{k=1}^{n_{0j}} R_{0jk} - \frac{1}{n_{1j}} \sum_{k=1}^{n_{1j}} R_{1jk} \right)}}{\sqrt{\sum_{j=1}^J a_j^2 \frac{1}{n_{0j} + n_{1j} - 1} \sum_{i=0}^1 \sum_{k=1}^{n_{ij}} (R_{ijk} - \bar{R}_{\bullet j \bullet})^2}}$$

where R_{ijk} is the rank of the observation X_{ijk} within strata j , $i=0,1$ denotes the treatment group, $j=1,..,J$ denotes the strata, $k=1,..,n_{ij}$ denotes the subjects within the i^{th} treatment group in the j^{th} strata and $\bar{R}_{\bullet j \bullet}$ is the average rank of all observations in strata j . This form of the test statistic was programmed into the SAS macro used for analyses.

Assuming no ties within the data, the simplified form of the variance, that is

$$\left[\sum_{j=1}^J a_j^2 \frac{1}{12} \cdot n_{0j} n_{1j} (n_{0j} + n_{1j} + 1) \right]$$

can be used.

Two weights have been used to combine results over strata:

$$\text{“Locally best”}: a_j = \sqrt{\frac{n_{0j}n_{1j}}{n_{0j} + n_{1j}}} \cdot \frac{1}{n_{0j} + n_{1j} + 1}$$

“Type II” (used for pooled analyses): $a_j = \sqrt{\frac{n_{0j}n_{1j}}{n_{0j} + n_{1j}}}$.

For large sample sizes (within each strata) the test statistic has a standard normal distribution; therefore the two-sided test would reject the null hypothesis if $|W^*| > u_{\alpha/2}$.

The test can easily be implemented using the SAS, PROC FREQ. The FREQ procedure is used with the TABLE statement options CMH2 and SCORES=MODRIDIT. The second CMH statistic, labeled "Row Mean Scores Differ" is the asymptotic test statistic.

As shown by [Koch et al 1982](#), the Van Elteren test is a member of a general family of Mantel-Haenszel mean score tests. For more information about the Van Elteren test and related testing procedure, refer to [Lehmann 1975](#), [Koch et al 1990](#).

5.4 Rule of exclusion criteria of analysis sets

The protocol deviations resulting in subjects' exclusion from analysis sets are defined below ([Table 5-2](#)). A complete list of the PDs can be found in the Edit Check Specifications document in CREDI.

Table 5-1 Deviation Codes Description

Deviation code	Text description	Deviation ID
1	SELECTION CRITERIA NOT MET	INCLXX ; EXCLXX
2	SUBJECT NOT WITHDRAWN AS PER PROTOCOL	WITHXX
3	PROHIBITED CONCOMITANT MEDICATION	COMDXX
4	TREATMENT DEVIATION	TRTXX
998	OTHER	OTHXX

Table 5-2 Subject Classification

Analysis Set	PD ID that cause subjects to be excluded	Non-PD criteria that cause subjects to be excluded
FAS	NA	Not randomized
SAF	NA	No double-blind study drug taken
[REDACTED]	[REDACTED]	[REDACTED]

5.5 Appendix A: Vital signs notable criteria

Table 5-3 Vital Signs Notable Criteria

Vital Sign Variable	Notable Criteria
Pulse (beats/min)	> 120bpm or Increase of ≥ 15 bpm from baseline

	or < 50bpm or Decrease of ≥ 15 bpm from baseline
Systolic BP (mmHg)	>180 mm Hg or Increase of ≥ 20 mm Hg from baseline Or < 90 mm Hg or Decrease of ≥ 20 mm Hg from baseline
Diastolic BP (mmHg)	> 105 mmHg or Increase of ≥ 15 mm Hg from baseline Or < 50 mmHg or Decrease of ≥ 15 mm Hg from baseline

5.6 Appendix B: Clinically notable laboratory values

Table 5-4 Clinically Notable Laboratory Values

Notable Values			
Laboratory Variable	Gender (M/F/Both)	Standard Units	SI Units
LIVER FUNCTION AND RELATED VARIABLES			
SGOT (AST)	F	>93 U/L	>93 U/L
SGOT (AST)	M	>111 U/L	>111 U/L
SGPT (ALT)	F	>90 U/L	>90 U/L
SGPT (ALT)	M	>123 U/L	>123 U/L
Total bilirubin	Both	>3.6 mg/dL	>63 μ mol/L
Alkaline Phosphatase	F	>832 U/L	>832 U/L
Alkaline Phosphatase	M	>1032 U/L	>1032 U/L
HEMATOLOGY VARIABLES			
Neutrophils	Both	<1.5x 10^3 /uL	<1.5x10 ⁹ /L

Note: Only selected lab parameters which have potential to be sensitive to AMG 334 exposure are listed.

5.7 Appendix C: Criteria for ECG abnormalities

[figure not shown]
Table 5-5 ECG Abnormality Ranges

[figure not shown]
ECG Parameter	Abnormality Flags	
	Absolute	Relative*
RR Interval	Low: < 600 msec ; High: > 1200 msec	Low: $\leq -20\%$; High: $\geq 20\%$
PR interval	Low: < 120 msec ; High: > 200 msec	Low: $\leq -20\%$; High: $\geq 20\%$
QRS Interval	Low: < 60 msec ; High: > 109 msec	Low: $\leq -20\%$; High: $\geq 20\%$

[figure not shown]
QT Interval	Low: < 320 msec ; High: > 450 msec	Low: \leq -20%; High: \geq 20%
QTcB Interval (Bazett's correction)	Low: < 320 msec ; High: > 450 msec	Low: \leq -20%; High: \geq 20%
QTcF Interval (Fridericia's correction)	Low: < 320 msec ; High: > 450 msec	Low: \leq -20%; High: \geq 20%

*Relative change from previous measurement in percent (%)

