#### 8.4.2    **Electrocardiogram (ECG)**

All ECGs must be recorded as outlined in the central ECG reading manual. The preferred sequence of cardiovascular data collection during study visits is ECG collection first, followed by vital signs, and blood sampling. The Fridericia QT correction formula (QTcF) as reported by the central reader should be used for clinical decisions.

Single 12 lead ECGs are collected. The original ECGs, printed on non-heat sensitive paper, appropriately signed, must be collected and archived at the study site.

Each ECG tracing must be labeled with study number, subject initials, subject number, date and time, and filed in the study site source documents. For any ECGs with subject safety concerns, two additional ECGs must be performed to confirm the safety finding and forwarded to the central ECG laboratory for assessment. Clinically significant ECG findings at randomization (pre-dose) must be discussed with the sponsor before administration of study treatment.

Clinically significant abnormalities must be recorded on the relevant section of the CRFs as appropriate.

**During COVID-19 pandemic**, if a subject cannot visit the site to have ECG recorded, or if visits by site staff to a subject's home are not feasible, the ECG may be performed locally and the result reported to the site. If local ECG is an option, each ECG tracing must be recorded as outlined in the central ECG reading manual, be labeled with study number, subject initials, subject number, date and time, and filed in the study site source documents. A communication process should be established with the patient so that the site is informed of the ECG result if performed locally.

If it is not possible to perform ECG locally, ECG must then be performed at the next on-site visit.

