### **ECG evaluations**

ECG intervals will be summarized by presenting summary statistics for changing from baseline values. The incidence rate of clinically notable ECG abnormalities will be summarized.

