2.1.3 Visit and analysis windows

Visit window for DB period

Since the actual visit for a subject may not exactly coincide with their targeted visit date, the actual visit date is mapped to a study visit.

The next study day window will be utilized to define study visit for data captured in DB period - lab, vital signs, ECG, C-SSRS and some PROs collected during office visits ([REDACTED] BDI-II, mMIDAS) before dose is administered.

Table 2-2 Study Visit Windows

Study visit	Target Day	Study Day
Baseline	See baseline assessment of the Study (Section 2.1.1.2 , baseline definition)	
Week 4	28	16 - 43
Week 8	56	44 - 71
Week 12	84	72 - 99
Safety follow-up (for safety endpoints)	Safety follow-up should be excluded from the analysis visit windows described above and summarized under 'safety follow-up visit' for safety analyses only. Target day: last IP dose date + 12 weeks	

For safety endpoints (like lab, vital signs) except ECG, when assessment value for scheduled visit and unscheduled visit are both present within the same analysis window, scheduled visit value should be used. Unscheduled visit will only be used when there is no measurement from the scheduled visit in the defined window. In case of multiple assessment values among the same type of visit (ie, scheduled vs. unscheduled) within the same analysis window, the closest to the scheduled visit day will be used. In case of equal distances (e.g same day), the latest assessment value will be used. The exception is an assessment at early study withdrawal visits along with another assessment within a window. In such cases, the early-withdrawal assessment will be used. For ECG, the same strategy will be applied except that no prioritization of scheduled vs unscheduled visit will be made.

In case of multiple assessments on the same day for PROs (including C-SSRS), the first assessment will be used. For C-SSRS, the first complete assessment performed with the electronic version ("Since last visit" recall period) or supplemental data collected on the CRF page will be used. In case of multiple days with assessments within an analysis window (for post-baseline visit) for PROs and C-SSRS, the day the closest to the scheduled visit day will be used.

Monthly Interval for Efficacy Endpoints (from eDiary)

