2.7.4 Other safety data

2.7.4.1 ECG and cardiac imaging data

The ECG measurements from this clinical study will be performed as per standard of care for routine safety monitoring, rather than for purposes of assessment of potential QTc effect.

Subject incidence of abnormal ECG diagnosis (see [Table 5-5](#)) will be summarized by treatment group and by visit.

However, since these evaluations may not necessarily be performed under the rigorous conditions expected to lead to meaningful evaluation of QTc data, these data are not expected to be useful for meta-analysis with data from other trials.

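### The SAP drops the protocol's ECG change-from-baseline summaries without declaring it, and its relative ECG flag is measured against the previous measurement, not baseline

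*SAP*

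**What the plan says.** Protocol 12.5.2, under ECG evaluations, plans two things. The first is that "ECG intervals will be summarized by presenting summary statistics for changing from baseline values". The second is the incidence of clinically notable ECG abnormalities.

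SAP 2.7.4.1 keeps only the second. It plans "Subject incidence of abnormal ECG diagnosis" by treatment group and visit, with abnormality defined in Table 5-5 (SAP 5.7, Appendix C). SAP section 4, on changes to the protocol's analyses, reads 'Not applicable'. SAP 2.12.2 takes the ECG part of the unblinded interim read-out from 2.7.4.1.

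Table 5-5 gives each interval an absolute and a relative flag. The absolute limits are "Low: < 600 msec ; High: > 1200 msec" for RR, "Low: < 120 msec ; High: > 200 msec" for PR, "Low: < 60 msec ; High: > 109 msec" for QRS, and 320 to 450 ms for QT, QTcB and QTcF. The relative flag is at or below −20%, or at or above +20%, and the footnote defines it as "Relative change from previous measurement in percent".

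Two other rules bear on this. For an ECG with a safety concern, Protocol 8.4.2 says that "two additional ECGs must be performed to confirm the safety finding". SAP 2.1.3 selects one value per visit window: "In case of equal distances (e.g same day), the latest assessment value will be used". For ECGs it gives scheduled tracings no priority over unscheduled ones.

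**The concern.** Two gaps compound each other. A planned protocol analysis is missing and the omission is not declared. What remains rests on a flag whose reference value moves with each ECG, so the flag shows whether one step was large and not whether the subject has moved away from the pre-treatment value.

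ECG is the outlier within the SAP. Table 5-3 includes change-from-baseline criteria for pulse and blood pressure. Laboratory data (SAP 2.7.3) and vital signs (SAP 2.7.4.2) both keep change-from-baseline summaries. SAP 2.1.1.2 already defines a safety baseline as the last evaluable value before the first dose. No reason is given for treating ECGs differently.

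At stake is which subjects count as abnormal in the ECG table, both in the study report and in the interim read-out. With no summary of change from baseline beside it, nothing else planned for ECGs would show a gradual shift inside the fixed limits.

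**Working it through.** The plan states no figure for this rule, so there is none to reproduce. The check applies Table 5-5 to short sequences of ECG values. The limits and the ±20% threshold come from Table 5-5. The interval values are illustrative assumptions.

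Relative change against the previous measurement = current / previous − 1. Against baseline = current / baseline − 1.

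**Where the absolute limits leave a gap.** A 20% rise stays inside the upper limit if baseline is at or below limit / 1.2:

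| Interval | Lower limit (ms) | Upper limit / 1.2 (ms) | Baseline range not covered for a 20% rise (ms) |
|---|---|---|---|
| QT, QTcB, QTcF | 320 | 450 / 1.2 = 375 | 320–375 |
| PR | 120 | 200 / 1.2 = 166.7 | 120–166.7 |
| QRS | 60 | 109 / 1.2 = 90.8 | 60–90.8 |
| RR | 600 | 1200 / 1.2 = 1000 | 600–1000 |

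**Drift (needs at least two post-baseline ECGs).** PR 135, 158, 185 ms:
- Against previous: 158/135 − 1 = +17.0%, then 185/158 − 1 = +17.1%. Neither is flagged.
- Against baseline: 185/135 − 1 = +37.0%. Flagged.
- All values lie within 120–200 ms, so there is no absolute flag.

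At the extreme, two steps of 19.9% give 1.199² − 1 = +43.8% with no relative flag.

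**Return to baseline (same requirement).** RR 1000, 780, 1000 ms:
- Against previous: 780/1000 − 1 = −22.0%, flagged Low; then 1000/780 − 1 = +28.2%, flagged High although the subject is back at baseline.
- Against baseline: −22.0%, flagged; then 0%, not flagged.

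A return is flagged only if the step back is itself at least 20%. After a fall f this means 1/(1 − f) − 1 ≥ 0.20, so f ≥ 16.7%. After a rise r it means 1 − 1/(1 + r) ≥ 0.20, so r ≥ 25%. A fall of 18% (PR 170, 139.4, 170 ms) is therefore unflagged going down (−18.0%) but flagged coming back (+22.0%). A rise of 22% (PR 150, 183, 150 ms) is flagged going up and not on the return (−18.0%).

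**Repeat ECGs (one visit is enough, but the result depends on the reading).** Baseline QTcF 360 ms; on treatment 440 ms, then repeats of 438 and 441 ms on the same day. The value used is the latest, 441 ms, which is below 450.
- Previous = preceding tracing: 441/438 − 1 = +0.7%. No flag. The first tracing was flagged (440/360 − 1 = +22.2%) but is not the value used.
- Previous = previous visit (here baseline): 441/360 − 1 = +22.5%. Flagged.

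**When the rule does no harm.** With one post-baseline ECG and no repeats, the previous measurement is the baseline and the two references agree.

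**The case against.** The strongest reply is that the flag is not the only safeguard. The absolute limits do not depend on any earlier ECG. Any 20% rise from a baseline QTcF above 375 ms exceeds 450 ms and is caught; QTcF 400, 445, 490 ms misses the relative flag but is flagged at 490. This stands. A reader might infer that a drift or a confirmed change goes wholly unflagged, and Table 5-5 does not support that: the loss is limited to the relative flag, for values inside the fixed limits.

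A reader might also infer that the protocol's own repeat procedure cancels the flag. That needs the previous measurement to mean the tracing just before, and the repeats to be taken on the same day. The SAP does not settle the first point and Protocol 8.4.2 does not settle the second. Because 2.1.3 selects one value per window and the table is by visit, the previous visit is an equally fair reading, and under it the case does not arise. That the footnote allows both readings is a reason to tidy it, not proof of failure.

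Drift and return need at least two post-baseline ECGs. The ECG row of Table 8-1 is not visible in the available text, so this remains an assumption.

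On importance, SAP 2.7.4.1 calls the ECGs routine safety monitoring and not an assessment of QTc effect. SAP 2.7 plans no between-arm safety tests. Clinically significant abnormalities are recorded on the CRF, and the DMC reviews cumulative safety data. Protocol 4.5 reports no evidence of cardiovascular risk to date, and its theoretical concern is vasodilation under ischemia, not interval change. These points limit the consequences. They neither withdraw the summary in Protocol 12.5.2, which lists ECG among its safety variables, nor give a reason for a moving reference.

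**Conclusion.** The point holds within stated limits. The firmest part needs no assumption about schedule or wording: the protocol's ECG change-from-baseline statistics are absent from SAP 2.7.4.1, and section 4 declares no change.

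The footnote is a real but conditional weakness. For values inside the absolute limits and with at least two post-baseline ECGs, a shift such as +37% in PR can pass without a flag, and a return to baseline can be counted as an abnormality. The repeat-ECG failure is possible on one reading of the footnote and absent on the other. The documents give no basis for estimating how many subjects would be affected, and the example values show only how the rule behaves. It is worth correcting because it changes who is counted in the only ECG analysis visible in the SAP, but it does not show that ECG safety goes unmonitored.

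**What to change.** - In Table 5-5, change the footnote so that the relative flag is the percentage change from baseline, with baseline the last evaluable pre-dose ECG as in SAP 2.1.1.2. This also removes the ambiguity about repeats.
- In SAP 2.7.4.1, restore the change-from-baseline summary statistics for ECG intervals from Protocol 12.5.2. The protocol's ECG paragraph does not say by visit; presenting them by visit and treatment group would match the SAP's other safety summaries.
- If the sponsor means to keep either departure, say so in SAP section 4 with the reason, and define the previous measurement.

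The cost is a footnote, a sentence and one standard table from data already collected. No visit, procedure or clinical rule changes. Because the interim read-out draws on 2.7.4.1, the edit carries through to it.
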